Analysis: Using information on resources required during appointments (e.g. personnel, duration, tests) collected via the PFHR patient questionnaires and HCP questionnaires and national unit costs,³⁸ we will calculate total healthcare costs per individual. We will estimate the impact of starting LLT on NHS costs over time, accounting for potential confounders. Our analysis approach to confounding and missing data will be similar to that described in Objective 1(a), using an appropriate model to accommodate the typically skewed cost data (e.g., generalised linear models).³⁹

Outputs

- Estimates of the use of NHS services by CYP with FH and their related costs
- Estimates of the effect of starting LLT on NHS costs related to service use

7.6 Objective 6: Estimate long-term health outcomes and NHS costs of starting LLT at different ages and LDL-C thresholds to identify a cost-effective approach to management

Method: To identify the cost-effective approach to initiating LLT at a range of ages and LDL-C thresholds, we will develop a new cost-effectiveness model. A decision model is required to estimate long-term reductions in CVD risk (which cannot be observed without decades of follow-up), given observed shorter-term LDL-C reductions. We will take the NHS perspective and express health outcomes primarily in quality-adjusted life years (QALYs). We will collaborate with the CYPAG, PCAG and clinical specialists to capture outcomes that matter to patients, families, clinicians, and healthcare commissioners. The cost-effectiveness analysis will be conducted and reported in accordance with current methodological guidance for cost-effectiveness analysis.⁴⁰

Analysis: The model structure will be based on our model developed to analyse the cost-effectiveness of alternative cascade screening protocols for FH.²⁵ We will link LDL-C to CVD risk based on the wellestablished concept that LDL-C increases CVD risk and this effect increases over time.¹⁷ Hence, the same LDL-C reductions over longer periods (from earlier LLT initiation) result in greater CVD risk reductions and more CVD events avoided. We will account for the impact of adherence in terms of its impact on LDL-C reductions from LLT (which are inherent to the estimates from the PFHR and CPRD data analyses) and via the proportion of CYP who continue LLT use into adulthood (estimated in Objective 3).

Decision options: We will evaluate a range of options for age and LDL-C at LLT initiation, highlighting combinations with major policy and clinical evidence, e.g., starting LLT at age 10 if LDL-C >3.5 mmol/L (as recommended by the European Atherosclerosis Society and the HEART UK Consensus Statement)^{5,15} compared with starting later or at lower or higher LDL-C thresholds.

We anticipate our model will comprise two modules:

Module (a) will quantify LDL-C, safety (i.e., adverse events, impact on health-related quality of life), costs during childhood/adolescence, and the likelihood of remaining on LLT into adulthood.

Module (b) will estimate long-term CVD consequences of raised LDL-C, potential long-term LLT sideeffects, and the impact of CVD and LLT side-effects on health-related quality of life, life expectancy, QALYs and NHS costs, over individuals' expected lifetime.

Module inputs: Data sources for the main inputs to (a) and (b) are tabulated below. Depending on whether data allows and the results from Objectives 1-3 and 5 analyses, individual inputs may be conditioned on pre-treatment LDL-C and age at LLT initiation. When multiple evidence sources are relevant, we will consider synthesising these or presenting alternative scenarios, depending on heterogeneity, quality, and relevance of the evidence.

Parameter	Source
Effect of LLT on LDL-C over time	 PFHR and CPRD analysis results (Obj. 1)
(proportional reduction)	 Systematic and pragmatic reviews (Obj. 1)
Proportion of young people	CPRD data analysis results (Obj. 3)
remaining on treatment at age 18	
Cost of LLT	PFHR data on the type of LLT prescribed (Obj. 1)

Inputs for Module (a) on CYP outcomes:

	Unit costs according to Drug Tariff
NHS costs of managing CYP with FH depending on whether they are treated with LLT or not	 NHS costs results based on data from patient and healthcare professional questionnaires (Obj. 5)
LLT adverse event rates and consequences	 LLT adverse event rates from PFHR and CPRD analysis results (Obj. 2) Systematic and pragmatic reviews (Obj. 2) Literature informing impact of adverse events on health-related quality of life
Health-related quality of life	 UK general population data (given that in our preparatory PPI work, advocates indicated that LLT initiation is not expected to significantly affect health-related quality of life, beyond the impact of potential LLT-associated adverse events)

We selected data sources for Module (b) given our recently completed study on FH.²⁵ This represents the most up to date and UK-relevant evidence on long-term outcomes in adult patients with FH and aligns, as far as possible, with cost-effectiveness analyses that informed the NICE FH guideline. The effect size between LDL-C over time and CVD risk later in life is a key driver of long-term benefits from treatment and requires follow-up beyond the reach of the PFHR follow-up that is possible in this 5-year study. A pragmatic review will be conducted to identify high-quality evidence, such as large individual patient data meta-analyses, that quantifies the impact of high LDL-C from childhood/early adulthood on later CVD morbidity and mortality.

Inputs for Module (b) on outcomes in adulthood:

Parameter	Source
Relationship between LDL-C over time and CVD risk later in life	Pragmatic review of studies evaluating the impact of high LDL-C from childhood/early adulthood on long-term CVD risk
Risk of CVD in adulthood	Risk equations from our previous work on a UK cohort of patients with FH (N=2,135, median follow-up 4.8 years)
Risk of non-cardiovascular death	General population statistics
Mortality risk following a first non- fatal cardiovascular event	Risk equations from our previous work, based on the risk observed in patients with FH and UK general-population study
Costs of LLT and of routine FH management	Current clinical guidelines for adults and expert advice
Costs of care post-cardiovascular events	Costs from an analysis of UK routine data of patients with coronary disease
Health-related quality of life prior to cardiovascular events	UK general population norms
Health-related quality of life post cardiovascular events	UK general population norms, adjusted for the impact of cardiovascular events based on previous cost-effectiveness analyses to inform NICE guidelines

Uncertainty: The model will reflect the parameter uncertainty in the module inputs via probabilistic sensitivity analysis. We will conduct extensive scenario analyses to the key assumptions. Examples include using estimates of effect of LLT on LDL-C from CPRD analysis rather than those obtained from PFHR in Objective 1, calculating NHS management costs based on clinical guideline recommendations rather than those estimated in Objective 5, using alternative relationships between LDL-C and long-term CVD risk identified by the pragmatic review.

Output

• Comparative cost-effectiveness of alternative policy options, interpreted considering the evidence base developed and identified across other previous objectives

8 User and Public Involvement

A study-specific Children and Young People's Advisory Group (CYPAG) and Parent and Carer Advisory Group (PCAG) will provide regular PPIE input across all study aspects via meetings and written/verbal input on design and feedback for study materials between meetings. A PPIE Strategic Adviser with expertise of working directly with children and young people and a PPIE Administrator are on the Study Management Group to ensure the responsibilities and contributions of the CYPAG and

PCAG are appropriately integrated into the development and outputs of the study. PPIE over 5 years has been appropriately funded in accordance with NIHR good practice for involving patients and will follow the Nottingham University Hospitals PPIE Standard Operating Procedure under guidance of the PPIE Strategic Adviser.

9 Dissemination and outputs

As members of key FH working groups, such as the National Genomic Medicine Service Alliance (GMSA) FH oversight committee and the NHSE FH Expert Advisory Group, we have a natural channel to inform national FH policy and engage key stakeholders. We will work closely with cholesterol charity HEART UK to advertise the study, provide regular public updates and progress newsletters, and disseminate learning from the study to NHS commissioners and policymakers. We will work with international colleagues in Australia and the USA to ensure our findings also inform international guidelines.

In addition to informing policymakers and patient advocates, all tiers of the study will be widely disseminated through peer-reviewed publications and conferences for scientific audiences. At 4-5 years of recruitment, a national summary report of the Register data will be disseminated to clinical sites. At 5 years, a project report will be submitted to the NIHR HTA.

10 Plan of investigation

Clinical Effectiveness, Safety and Adherence

Analysis of ALSPAC & CPRD databases (3-12 months) Training clinical staff on PFHR data entry (6-12 months) PFHR database retrospective data collection (8-18 m) & preliminary analysis (12-32 m) PFHR database prospective data collection (8-48 m) & main analysis (retrosp+prosp data) (18-54 m) Evidence reviews (6-12 m) & updated searches and analyses (36-42 m)

Questionnaires & Qualitative Studies

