6.4.1 Protocol summary

Currently, treatment of paediatric FH remains secondary and tertiary care led. This study will collect questionnaire and interview data from HCPs currently involved in the clinical diagnosis and followup management of CYP with FH, in centres throughout the UK. It will provide data on and insight into current treatment practices in contemporary FH management in CYP, from lifestyle management to LLT, and from diagnosis to transfer to adult services. It will provide information on variation in clinical practice (routine practice/criteria on decisions to initiate LLT, treatment targets, adherence monitoring, starting dose, changing dose, and type/frequency of specialist healthcare provision) and the factors that influence this. Information will be used to describe the current clinical landscape and as variables in the PFHR analyses of clinical and cost-effectiveness, to account for clinical variation across sites in factors such as treatment targets.

There are no available estimates of the number of HCPs working in paediatric FH in the UK. Based on the existing PFHR clinical network and informal professional networks organised by the UK cholesterol charity HEART UK, we estimate 50-100 HCPs will complete questionnaires and we will interview 30 HCPs.

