6.4.1 Participant withdrawal

Participants will be free to withdraw (i.e., to stop completing the questionnaire or stop the interview) at any time without giving a reason. In addition, the research team may discontinue a participant's participation from the study at any time they consider it necessary for any reason including:

- Withdrawal of consent
- Incomplete/unusable data

When a participant withdraws from further participation, any information already obtained will be retained and may still be used in the final study analyses (this will be made clear in information sheets and consent forms).

7 Analysis

7.1 Objective 1: Estimate absolute and relative reductions in LDL-C, and in cumulative LDL-C, achieved in current practice with LLT, and whether these vary by age and LDL-C at initiation of LLT

Methods: We will evaluate the effectiveness of initiating LLT at different ages and LDL-C thresholds (at baseline) on LDL-C levels measured at **routine follow-up visits recorded in the PFHR** (and **secondarily in the CPRD FH population**). We will:

(a) estimate absolute and % reductions in LDL-C from pre-treatment levels, which will then be incorporated into the economic model,

(b) estimate cumulative LDL-C and time-weighted average (TWA) LDL-C, the latter providing an estimate of average LDL-C burden over childhood and adolescence,

(c) evaluate achievement of treatment targets, using expert-consensus recommendations for FH^{5,15} and average age-specific LDL-C levels in the general (non-FH) population (derived from CYP in the ALSPAC cohort),

(d) address potential evidence gaps by updating our current systematic review of statin trials in children with FH² to include all LLT and a new pragmatic review of high-quality observational evidence.

Analysis (a): **Absolute (mmol/L) and % reductions in LDL-C** from pre-treatment levels associated with age and LDL-C at LLT initiation will be estimated using a linear mixed-effects model. A multi-level structure will be used to account for children being grouped at clinical sites, with site as a random effect.

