LDL-C changes in those exposed to LLT will be compared with changes in those never exposed or unexposed up to a certain age, measured as the difference between the earliest and later follow-ups. We will use inverse probability of treatment weighting techniques^{28,29} to balance exposed and unexposed groups according to both baseline and time-varying measured confounders: family history of CVD and/or FH in family, gender, genetic testing, body mass index (BMI), ethnicity, other health conditions, reasons for not being on LLT or non-adherence, process factors such as attendance frequency, and socioeconomic deprivation (using post-code linkage to index of multiple deprivation).

We will primarily estimate intention-to-treat effects, i.e. the effect of prescribing LLT to children with FH on LDL-C levels.³⁰ We will then estimate per-protocol effects, which corresponds to the effect of continuously taking LLT during the following period. Potential treatment non-adherence and loss to follow-up will be accounted for via censoring weights.³⁰ Missing data in both the LDL-C outcomes and confounders will be addressed using multiple imputation.

We will conduct sensitivity analyses to assess the extent to which the effects of age and LDL-C at initiation are robust to potential unmeasured confounding. We will adopt the E-value approach,³¹ which essentially explores how strong (association with both LLT initiation and LDL-C outcomes) the unmeasured confounders need to be to change the study conclusions. These analyses will be informed by discussions with clinical specialists and PPIE groups, and the HCP questionnaire.

This will be a descriptive analysis with the ultimate aim to derive effectiveness estimates that will feed into the cost-effectiveness model, where uncertainty will be fully propagated.³² However, initial assessment, based on pre- and post-puberty in current PFHR data shows children initiating LLT before age 12 years achieved a mean reduction in LDL-C of 2.199 after initial mean levels of 6.115 (pooled SD=2.51) and those initiating LLT at 12 or older achieved a mean reduction in LDL-C of 1.748 after initial mean levels of 5.570 (pooled SD=1.53). Demonstrating this difference at 90% power and 0.05 significance level with a 60-40 allocation ratio (as in the current Register) would require 560 children initiating LLT before age 12 and 376 initiating LLT at 12 or older, which is within our planned recruitment target.

Secondary analyses:

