2. **CPRD** data on hospital admissions or general practice attendance will be used to assess sideeffects and adverse events. We will use post-marketing side-effects reported for each LLT type (e.g., headache, dizziness, unusual weakness, sleep problems). CPRD will provide a large sample to assess adverse events (e.g., rhabdomyolysis) as these will be extremely rare according to current evidence in adults.³⁵ Safety across childhood and into early adulthood will be assessed (with 42% of children with FH having CPRD records into adulthood).

3. Potential gaps will be addressed by the **systematic and pragmatic reviews**, as described in objective 1, that will include short and longer-term rare or serious side-effects of LLT including ezetimibe.

Analysis: Among children on LLT, liver enzyme (transaminases) measures >2.5 times the upper limit of normal before and after puberty will be described according to LLT type (of statin and more rarely used medications such as ezetimibe) and dose. Logistic regression models will be used to adjust for clinical and sociodemographic factors.

Age at first menstruation, weight-for-age and weight-for-height z-scores (BMI in adolescents) according to LLT exposure (type, dose, age at initiation) will be modelled using generalized estimating equations/growth models adjusting for clinical and sociodemographic factors.

Incidence rates of side-effects and adverse events will be described according to LLT exposure (type, dose, age at initiation) and Poisson regression will be used to adjust for clinical and sociodemographic factors.

Outputs

- Incidence of side-effects and adverse events
- Effects of LLT on growth and development
- Parameters for economic model (Objective 6): LLT adverse event rates

7.3 Objective 3: Estimate LLT adherence at different ages and characterise reasons for variations in adherence

Methods: We will measure adherence and characteristics related to variation in adherence using:

(a) Adherence captured at **routine follow-up visits recorded in the PFHR.** Based on discussions with our clinical specialist collaborators and Nottingham CYPAG and our PPIE group, these items will indicate recent adherence and reasons for sub-optimal adherence.³⁶

(b) **Patient questionnaires at baseline, 8, 16, 24 months** to obtain changes in adherence over time incorporating the Medication Adherence Report Scale.²⁷ The study CYPAG and PCAG will support interpretation of the questionnaire results.

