Should there be any subsequent amendment to the final protocol, which might affect a participant's participation in the study, continuing consent will be obtained using amended consent/assent forms which will be signed by the participant.

STUDY/ REGIMEN

Clinical data collection: Following provision of consent, no active involvement/follow-up is required by the participant individual with FH or their parent/guardian. Clinicians enter clinical data based on medical notes and clinical consultations from the course of their routine clinical care for the individual with FH. The period of data collection will depend on the paediatric clinical follow-up of the patient with FH and will typically be up to age 18 years but will vary based on the clinical service provision from approximately age 16 to age 25 years.

At the point of providing consent for clinical data collection, participants can additionally express an interest in being contacted for involvement in further research and will provide their contact details and preferred method of contact. They will be given the choice to provide one or more of the following: email address, telephone number, postal address, and a preference for one or more of the following: contact via email, text message, telephone call or by post.

Questionnaire data collection: Following provision of consent, participant individuals with FH who are age 16 years or older or parents/guardians of individuals with FH who are younger will complete a baseline questionnaire (Q1) using the REDCap web application or a paper questionnaire. At 8, 16, and 24 months, follow-up questionnaires (Q2, Q3, Q4) will be sent to the participant for completion with automatic reminders at 2 weeks and 4 weeks automatically generated by the REDCap system or via contact by the Study Manager/Administrator or nominee.

Information at the start of the questionnaire will explain to parents/guardians that they can fill out the questionnaire independently or with input from their child with FH. Information at the

Page 20 of 37

Paediatric FH Register Study Protocol IRAS ID: 324246 18 June 2024 Final version 2.0

start of the questionnaire will explain to individuals with FH who are age 16 years or older that they can fill out the questionnaire independently or with input from their parent/guardian. Participants will be asked to record whether it was filled out independently or with a family member.

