If insecure access to the REDCap consent, clinical or questionnaire data entry web interfaces was discovered from an external unauthorised source, the REDCap data entry interface would be suspended until methods of access were deemed secure.

Due to the nature and use of the data that is due to be collected as part of this study, there is no criterion for terminating the study.

ANALYSES

Methods

Statistical support for appropriate monitoring of study participant numbers, data completeness, data quality and the interview sampling frame will be provided by the Study Statistician at the

Page 21 of 37

Paediatric FH Register Study Protocol IRAS ID: 324246 18 June 2024 Final version 2.0

University of Nottingham with oversight of the Study Leads. Monitoring and analysis protocols will also be shared with the SSC and DMEC for their review.

Quantitative analyses will be conducted using Stata and R software by researchers with epidemiological, statistical and health economics expertise. Qualitative analyses will be conducted using NVivo software by researchers with qualitative methodology and analysis expertise.

Clinical effectiveness analysis

For the primary assessment of clinical effectiveness, absolute (mmol/L) and percentage reductions in LDL-C from pre-treatment (LLT) concentration levels will be estimated using a linear mixed-effects model. A multi-level structure will be used to account for patients being grouped at clinical sites, with site as a random effect. LDL-C changes in those exposed to LLT will be compared with changes in those never exposed or unexposed up to a certain age, measured as the difference between the earliest and later follow-up measurements. We will use the inverse probability of treatment weighting techniques¹⁵ to balance exposed and unexposed groups according to both baseline, and time-varying measured confounders: family history of CVD and/or FH in the family, gender, genetic testing, body mass index (BMI), ethnicity, other health conditions, smoking status, socioeconomic deprivation (using post-code mapped to index of multiple deprivation), reasons for not being on LLT or non-adherence, process factors such as attendance frequency.

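### Analysis (a) does not tie LDL-C change to time since LLT initiation, so the reduction by starting age can mix starting age with time on treatment

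*Protocol*

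**What the plan says.** Section 7.1, Analysis (a), states that absolute and percentage reductions "from pre-treatment levels associated with age and LDL-C at LLT initiation will be estimated using a linear mixed-effects model", with clinical site as a random effect. Children exposed to LLT are compared with children never exposed, or not exposed up to a certain age, and the change is "measured as the difference between the earliest and later follow-ups". The clinical effectiveness section of the appendix register protocol gives the same definition in nearly the same words.

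The weighting list covers "family history of CVD and/or FH in family, gender, genetic testing, body mass index (BMI), ethnicity, other health conditions", together with "reasons for not being on LLT or non-adherence, process factors such as attendance frequency" and deprivation; the appendix adds smoking. Its stated purpose is to balance exposed and unexposed groups. On the estimand, section 7.1 says: "We will primarily estimate intention-to-treat effects, i.e. the effect of prescribing LLT to children with FH on LDL-C levels".

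On the length of observation, the STUDY/REGIMEN section of the appendix says that data collection "will typically be up to age 18 years but will vary based on the clinical service provision", from about 16 to 25 years.

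The result goes to section 7.6, where Module (a) needs the proportional effect of LLT on LDL-C over time. Section 7.6 allows inputs to be conditioned on pre-treatment LDL-C and on age at initiation. It does not mention time since initiation as a conditioning variable.

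**The concern.** The core question is how effectiveness depends on the age at which LLT is started. If change is taken at whatever later visits exist, and these tend to lie further from the start of treatment in early starters, a difference by starting age may partly be a difference in how long the children had been treated when measured.

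The baseline is loose as well. Reductions are said to be from pre-treatment levels, but change is counted from the earliest follow-up. For a child diagnosed some time before treatment, the earliest value need not be the last value before treatment.

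At stake is the input to the economic model. Section 7.6 already gives longer treatment its own credit, because the same LDL-C reduction over more years prevents more events. The model therefore needs the reduction at a stated time after starting, not one that already carries an unknown amount of treatment time.

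**Working it through.** **1. The plan's own figure.** Section 7.1 gives a mean reduction of 2.199 from 6.115 mmol/L (SD 2.51) for starts before 12, and 1.748 from 5.570 (SD 1.53) for starts at 12 or older. It uses 90% power, a 0.05 level and 60-40 allocation, and states 560 and 376 children.
- Difference: 2.199 − 1.748 = 0.451 mmol/L.
- Root-mean-square SD: √[(2.51² + 1.53²)/2] = 2.079.
- Later starters: (1 + 1/1.5) × (1.960 + 1.282)² × 2.079² / 0.451² ≈ 372. Early starters: 1.5 × 372 = 558.

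This reproduces the stated sizes closely (two-sided). The calculation uses the crude difference and takes no account of time on treatment.

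**2. The same difference on the percentage scale.**
- 2.199/6.115 = 36.0%; 1.748/5.570 = 31.4%; gap 4.6 points.
- At an equal 31.4% reduction, the higher baseline alone gives 0.314 × 6.115 − 1.748 = 0.171 mmol/L, leaving 0.451 − 0.171 = 0.280. LDL-C at initiation is in the planned model, so that model should handle the 0.171. It names no term that would handle time on treatment.

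**3. Observable time on treatment.** With collection ending at 18, the ceiling is 18 minus starting age. Section 6.1 gives a mean starting age of 11 (SD 3).

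| Age at start | Ceiling, years |
|---|---|
| 8 (mean − 1 SD) | 10 |
| 11 (mean) | 7 |
| 14 (mean + 1 SD) | 4 |
| 15 | 3 |

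A different common end age moves every row equally, so the 6-year spread between starts at 8 and 14 remains. These are ceilings, not averages. Existing Register follow-up averages 2.9 years (SD 1.8), and up to 3.5 years are to be added. The documents do not give time on treatment by starting age.

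**4. What would matter.** Assumption, not in the documents: the reduction drifts by *g* points of baseline per year since initiation, early starters are measured *d* years later on average, and starting age has no effect. Shift = *g*/100 × *d* × 6.115.

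| *g* | *d* | Shift, mmol/L | Share of 0.451 |
|---|---|---|---|
| 0.5 | 1 | 0.03 | 7% |
| 1 | 2 | 0.12 | 27% |
| 2 | 2 | 0.24 | 54% |
| 3 | 2 | 0.37 | 81% |

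On the percentage scale, 4.6/2 = 2.3 points a year over two extra years equals the whole gap. The sign is open. Treatment changes could deepen the reduction over time. Section 5.1, however, cites long-term adherence as low as 20% about 10 years after initiation, and under intention-to-treat that would make it fade.

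**5. The baseline.** Section 6.1 gives a mean age at diagnosis of 9 and at initiation of 11. These averages cover partly different children, but they suggest that the earliest and the last pre-treatment measurements can be some two years apart.

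**The case against.** The strongest reply is about the estimand. Objective 1 concerns reductions achieved in current practice, and the primary effect is that of prescribing LLT. Longer treatment and later treatment changes follow from starting earlier, so they belong to the effect of an age policy. That is right, and it is why the pooled estimate should stay.

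It also defeats three stronger readings that a reader might infer:
- **That dose escalation in early starters will be mistaken for a benefit of starting early.** The documents do not show that early starters are escalated more. Under the stated estimand, later escalation is part of the strategy.
- **That LLT type and dose are wrongly missing from the weighting list.** The weights balance exposed against unexposed children, and unexposed children have no type or dose. Objective 2 does use them ("Incidence rates of side-effects and adverse events will be described according to LLT exposure (type, dose, age at initiation"), but there the task is to describe harm. Adjusting for or stratifying on post-initiation dose as an ordinary covariate would condition on choices that may respond to LDL-C. Dosing practice enters at site level through the professionals' questionnaire ("adherence monitoring, starting dose, changing dose, and type/frequency of specialist healthcare provision").
- **That benefit, harm and cost refer to different regimens.** When the LDL-C effect and the drug cost both come from the Register, they average over the same prescribing mix.

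A further reply is that a mixed model with several later follow-ups can carry a time term, that Module (a) asks for an effect over time, and that the detail belongs in the SAP. The text does not exclude such a term. But the protocol defines the change score in two places without a time origin, and comparing starting ages at unequal times since initiation remains a fault even if all later treatment belongs to the strategy.

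**Conclusion.** The point holds for time alignment only. As written, the reduction by age at initiation can mix starting age with time on treatment, because change has no origin at LLT initiation and the observable treatment period shrinks as starting age rises. Neither direction nor size can be established from the documents. The illustrative range of 0.03 to 0.37 mmol/L rests on assumed drift and assumed extra time, with either sign possible, and the 0.451 mmol/L it is set against is a crude preliminary difference, not the planned weighted estimate. The pooled estimate is not invalid for its stated purpose. What is missing is a version that compares starting ages at the same time since starting, which is what Module (a) needs.

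**What to change.** In section 7.1, Analysis (a), and in the clinical effectiveness section of the appendix:
- For treated children, define change from the last pre-treatment LDL-C.
- Include time since initiation in the mixed model, with its interaction with age and LDL-C at initiation.
- Give unexposed children a matching index date, so that both groups are measured from a comparable origin.
- Report reductions at common times since initiation, for example within 12 months and then yearly, and use them for the Module (a) input on the LLT effect over time.
- Keep the pooled intention-to-treat estimate as the description of current practice.
- As context, LLT type and dose at initiation may be tabulated by age at initiation. Do not adjust for or stratify on post-initiation dose as an ordinary covariate.

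The treatment start date and the pre-treatment LDL-C are already prioritised in the inclusion criteria (section 6.1.3 and the appendix), so no new data items are needed. The cost is somewhat more modelling and lower precision at later times for late starters.
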